### Observations:

1. If the standard deviation of baseline WAIS-III PIQ and six month WAIS-III PIQ is 15 in both arms and the correlation between repeated WAIS-III PIQ measurements is 0.70 in both arms, then the power to detect a five-point difference is 22%.
2. If the standard deviation of baseline WAIS-III PIQ and six-month WAIS-III PIQ is 15 in both arms but the correlation between repeated WAIS-III PIQ

measurements is 0.80 in both arms, then the power to detect a 10-point difference is 82%.

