**TABLE 13.2 Sample Size Calculations for a 2-Sided t-test with an SD of 20 and  $n_2 = 0.3n_1$**

Difference in mean WAIS-III Performance IQ between adults with SCD and the control group.	Sample sizes required in each group (2-sided) Cases, Controls*	Power
8	213, 64	0.80
8	244, 74	0.85
8	285, 86	0.90
8	352, 106	0.95
10	137, 42	0.80
10	156, 47	0.85
10	183, 55	0.90
10	226, 68	0.95
15	61, 19	0.80
15	70, 21	0.85
15	81, 25	0.90
15	101, 31	0.95

\* *Sample Size Estimates Assuming 3 Controls for Every 10 Cases. (These do not take data loss into account).*

Observations:

1. If the standard deviation of the WAIS-III is no greater than 15 and the true difference in WAIS III group means is at least eight, then using 120 SCD patients and 36 controls results in at least 80% power for the primary hypothesis.
2. If the standard deviation of the WAIS-III is no greater than 20 and the true difference in WAIS III group means is at least 15, then using 101 SCD patients and 31 controls results in at least 95% power for the primary hypothesis (see Table 13.2).

In order to have sufficient power for the primary hypothesis and sufficient patients recruited for the 4th secondary hypothesis (transfusion study) we would need to enroll 150 patients and 45 controls. Assuming an 80% completion rate, 120 patients and 36 controls would complete the baseline evaluation. (Please refer to observations 1 and 2 above for power estimates.) Assuming a normal distribution, 60 of the 120 patients will have WAIS-III PIQ scores at or below the predicted mean of 85. These patients would be approached to participate in the transfusion study. Assuming 60% would agree to participate and again assuming a completion rate of 80%, 36 patients would be randomized to either the chronic transfusion arm or the standard care arm and 30 would complete the protocol (allowing for 15 in each group).

For power calculations and statistical analysis the 4th secondary hypothesis, the transfusion arm will have a mean WAIS-III PIQ change score that is different than the mean change score in the control arm, can be expressed:

$$H_0: \mu_{\text{diff, trt}} - \mu_{\text{diff, control}} = 0$$

$$H_a: \mu_{\text{diff, trt}} - \mu_{\text{diff, control}} \neq 0.$$

We will use a 2-sample comparison t-test framework for power calculations. To estimate the power of the t-test given 15 subjects per arm, we used the following normal approximation:

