1. Choose a mean change score difference under the alternative,  $H_{a, \text{diff}}$ .

2. Calculate the expected variance of the within subject change score:

$$V(d_i) = V(\text{WAIS}_{i, \text{After}}) + V(\text{WAIS}_{i, \text{Before}}) - 2 \cdot \rho_{\text{WAISAfter, Before}} \sqrt{V(\text{WAIS}_{i, \text{After}})} \cdot \sqrt{V(\text{WAIS}_{i, \text{Before}})}$$

where  $V(\text{WAIS}_{i, x})$  is the WAIS variance for the  $i^{\text{th}}$  subject at time  $x$ .

3. Calculate the expected variance of difference in mean change scores:

$$V(\bar{d}_{\text{trt}} - \bar{d}_{\text{control}}) = V(d_i) \left( \frac{1}{15} + \frac{1}{15} \right)$$

4. Using an alpha of 0.05 calculate the critical value needed to reject the hypothesis under the null:  $0 + 1.96 \cdot \sqrt{V(\bar{d}_{\text{trt}} - \bar{d}_{\text{control}})} = a_{\text{crit}}$

5. Calculate power:

$$\Pr \left[ \left| \bar{d}_{\text{trt}} - \bar{d}_{\text{control}} \right| > a_{\text{crit}} \mid E(\bar{d}_{\text{trt}} - \bar{d}_{\text{control}}) = H_{a, \text{diff}} \right] = 1 - \Phi \left[ \frac{-a_{\text{crit}} - H_{a, \text{diff}}}{\sqrt{V(\bar{d}_{\text{trt}} - \bar{d}_{\text{control}})}} \leq Z \leq \frac{a_{\text{crit}} - H_{a, \text{diff}}}{\sqrt{V(\bar{d}_{\text{trt}} - \bar{d}_{\text{control}})}} \right]$$

where  $\Phi$  is the cumulative distribution function for the normal distribution.

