Cortical gray matter and hippocampal volume will demonstrate a more significant correlation with executive and memory cognitive functions than the correlation of WML or lacunar infarcts with these same cognitive functions.

The statistical analysis will not involve a formal hypothesis test, but in statistical terms the hypothesis can be written as:

$$H_0: \rho_{\text{MRI-Nptest-Vol}} - \rho_{\text{MRI-Nptest-Reg}} = 0$$

$$H_a: \rho_{\text{MRI-Nptest-Vol}} - \rho_{\text{MRI-Nptest-Reg}} \neq 0.$$

For this analysis, we will descriptively compare Spearman or Pearson correlations.

The last secondary hypothesis involves randomizing 36 people who had a baseline WAIS-III PIQ score  $\leq 90$  to two treatment groups. We will treat one group with transfusion for 6 months and the other group with standard care for six months. After the six months of treatment we will perform a before and after comparison of the WAIS-III PIQ results, using within subject WAIS-III PIQ change scores as the outcome. We expect that on average patients who receive transfusion will show at least a five-point improvement when retested after six months of transfusion. Although this secondary hypothesis expresses the expected direction of effect independently of the observed affect in the control group, the statistical analysis will follow common practice and first use a 2-sided hypothesis test with an alpha of 0.05 to compare the mean within subject WAIS-III PIQ change score in the two groups. Second, we will calculate a 95% CI for the true effect of transfusion on WAIS-III PIQ within subject change scores for the group who received transfusion. We will use either a t-test, a Wilcoxon Two-Sample test, or a regression model to test the hypothesis. For statistical analysis we can express this secondary hypothesis as the mean within subject change score in WAIS III PIQ for the transfusion group will be different than the mean within subject change score in the control group:

$$H_0: \mu_{\text{diff, trt}} - \mu_{\text{diff, control}} = 0.$$

$$H_a: \mu_{\text{diff, trt}} - \mu_{\text{diff, control}} \neq 0.$$

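### The Phase II power of 82% comes from a normal approximation that is slightly optimistic at 15 per arm; the t-test it describes has 79.6%

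*Protocol*

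**What the plan says.** For the fourth secondary hypothesis, Protocol section 13.1 adopts a two-sample t-test framework and then states: "To estimate the power of the t-test given 15 subjects per arm, we used the following normal approximation". The steps follow in full. The change-score variance is built from the two WAIS-III PIQ variances and their correlation, then scaled to the difference of two means of 15. The next step reads "Using an alpha of 0.05 calculate the critical value needed to reject the hypothesis under the null", and the formula beside it multiplies the standard error by 1.96. The last step reads power from the normal distribution.

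Two results are printed under Observations. The first takes SD 15 and a correlation of "0.70 in both arms, then the power to detect a five-point difference is 22" per cent. The second begins "If the standard deviation of baseline WAIS-III PIQ and six-month WAIS-III PIQ is 15 in both arms but the correlation" and continues that if the correlation between repeated "measurements is 0.80 in both arms, then the power to detect a 10-point difference is 82" per cent.

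Section 13.2 says the analysis will "first use a 2-sided hypothesis test with an alpha of 0.05 to compare the mean within subject WAIS-III PIQ change score in the two groups". It leaves three methods open: "We will use either a t-test, a Wilcoxon Two-Sample test, or a regression model to test the hypothesis".

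The figure of 15 per arm comes from recruitment and completion assumptions in section 13.1: "36 patients would be randomized to either the chronic transfusion arm or the standard care arm and 30 would complete the protocol".

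**The concern.** A cut-off of 1.96 belongs to a test whose variance is known. The t-test estimates the variance from the 30 change scores, and its two-sided 5% critical value on 28 degrees of freedom is 2.048. Putting 1.96 in its place overstates power, and the effect is largest in small samples such as this one.

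The two observations are the protocol's only numerical statements of what the randomized phase could detect, and 82% is the favourable one. A reader weighing a null pilot result might rely on it. The figure should therefore describe the test it is said to describe.

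**Working it through.** **Inputs, all from Protocol sections 13.1 and 13.2.** SD 15 at both time points in both arms; correlation 0.80 with a 10-point difference, or 0.70 with a 5-point difference; 15 per arm; two-sided alpha 0.05.

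**Step 1: variance of the change score.** V = 15² + 15² − 2ρ·15·15 = 450(1 − ρ).
- ρ = 0.80: V = 90, SD of change 9.487.
- ρ = 0.70: V = 135, SD of change 11.619.

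**Step 2: standard error of the difference in mean change.** SE = √(V × 2/15).
- ρ = 0.80: √12 = 3.464.
- ρ = 0.70: √18 = 4.243.

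**Step 3: reproduce the printed powers with the protocol's own method.** Power = Φ(δ/SE − 1.96) + Φ(−δ/SE − 1.96).
- 10 points, ρ = 0.80: δ/SE = 10/3.464 = 2.887; Φ(0.927) = 0.823, with a negligible second term. Result 82.3%; printed 82%.
- 5 points, ρ = 0.70: δ/SE = 5/4.243 = 1.179; Φ(−0.781) + Φ(−3.139) = 0.2173 + 0.0008 = 0.218. Result 21.8%; printed 22%.

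Both printed figures follow exactly from the stated method.

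**Step 4: the same inputs under the t-test.** Use the noncentral t distribution with 28 degrees of freedom, critical value 2.048 and noncentrality δ/SE.

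| Scenario | Printed | Normal, recomputed | t-test, 28 df | Printed minus t |
|---|---|---|---|---|
| 10 points, ρ = 0.80 | 82% | 82.3% | 79.6% | 2.4 points |
| 5 points, ρ = 0.70 | 22% | 21.8% | 20.7% | 1.3 points |

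**Step 5: the other methods that section 13.2 permits, at 10 points and ρ = 0.80.**
- Wilcoxon test, simulated with 400,000 trials and normally distributed change scores: 76.2% (exact, or asymptotic with continuity correction) to 77.6% (asymptotic without correction). The corresponding range for 5 points and ρ = 0.70 is 18.7% to 19.9%.
- Regression model. The protocol gives no form, so adjustment for baseline PIQ is an assumption here. The residual SD is 15√(1 − 0.80²) = 9, the SE is 9√(2/15) = 3.286 and the noncentrality is 3.043. Power is 83.6% on 28 degrees of freedom, or 83.5% on 27 to allow for the covariate. Chance baseline imbalance is ignored.

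The printed 82% therefore lies inside the range that the three permitted methods span, roughly 76% to 84%, but it is not the power of the t-test.

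**The case against.** The strongest reply is that nothing is miscalculated. The protocol calls its method a normal approximation, prints every step including the 1.96, and reports figures that follow from it. That stands: the defect is a loose approximation at this sample size, not an arithmetic slip.

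A reader might go further and infer that Phase II fails to reach 80% power as promised. The protocol does not support this. It sets no power target for Phase II, calls it a pilot, and says in the Synopsis that the secondary hypotheses concern estimation. It also prints 22% power for a five-point difference, which is the effect it expects, so it does not present the phase as well powered. Besides, 79.6% rounds to 80%.

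A reader might also infer that 82% is out of reach under any permitted analysis. That fails too, because a baseline-adjusted regression would exceed it under the assumption above. The Wilcoxon figures are no general verdict on that test either: they hold for normal change scores, and with skewed or heavy-tailed scores the comparison with the t-test can reverse.

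Finally, the gap is small beside the uncertainty in the inputs. At 10 points, lowering the correlation from 0.80 to 0.70 takes the normal-approximation power from 82.3% to 65.4%. This is fair, and it limits the importance of the point. It does not make 82% the right figure for the t-test under the inputs stated.

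**Conclusion.** The point holds as a minor overstatement. For the t-test that section 13.1 names, with 15 per arm, SD 15 and correlation 0.80, power for a 10-point difference is 79.6%, not 82%. For 5 points and correlation 0.70 it is 20.7% against 22%, which makes no practical difference. These figures assume normal change scores, equal variances and exactly 15 completers per arm.

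The design is unaffected. Fifteen per arm rests on how many patients are expected to agree and to complete, not on the power figure. The message for the expected five-point effect, about one chance in five of detection, is the same under either calculation.

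**What to change.** In Protocol section 13.1, replace the last two steps of the Phase II power calculation with the noncentral t distribution on 28 degrees of freedom. Restate the observations as about 21% (5 points, correlation 0.70) and about 80% (10 points, correlation 0.80).

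Optionally, add a sentence that power depends on which method in section 13.2 is used: at 10 points and correlation 0.80, about 76–78% for the Wilcoxon test under normal change scores, and about 83–84% for a regression adjusted for baseline, if that is the form intended.

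The cost is a few words and slightly less favourable printed figures. Sample size, procedures and analysis stay as they are.

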## 13.2 STATISTICAL METHODS

The primary clinical hypothesis is that the mean score for adult patients with SCD on the WAIS-III PIQ scale will be at least one standard deviation below the mean score of a group of community controls matched for site, age, and education. We expect the adult patients with SCD will have a mean WAIS-III PIQ of 85 or less and the community control group will have a mean of 100. Although the primary hypothesis expresses the expected direction of effect, the statistical analysis will follow common practice and use a 2-sided hypothesis test with an alpha of 0.05.

To test the primary hypothesis, we will use a GLM to model the data. At each site participating in this study we will match the patients using a ratio of 3 patients to 1 community controls, but if necessary we will still statistically control for site, age, sex, and education. Model selection techniques will be used to determine the most parsimonious models. For statistical analysis we express the primary hypothesis, adult SCD patients will have an adjusted mean WAIS-III PIQ different from the community based control group adjusted mean WAIS-III PIQ (based on the final model):

$$H_0: \text{Adj\_}\mu_{\text{SCD}} - \text{Adj\_}\mu_{\text{control}} = 0$$

$$H_a: \text{Adj\_}\mu_{\text{SCD}} - \text{Adj\_}\mu_{\text{control}} \neq 0.$$

The first secondary hypothesis is the same as the primary hypothesis with other NP tests being used as the response; therefore, the analysis for these hypotheses will be the same as the primary hypothesis.

The 2nd secondary hypothesis is that patients with SCD and abnormal MRIs will have a higher proportion of abnormal NP test results than the patients with SCD and normal MRIs. The statistical analysis of this hypothesis will follow common practice and use a 2-sided hypothesis test with an alpha of 0.05. For statistical analysis we express this secondary hypothesis as:

Cortical gray matter volume, hippocampal volume, white matter lesions (WML), cortical strokes, and lacunar infarcts will correlate with cognitive function (memory and executive function).

$$H_0: \rho_{\text{MRI-NPtest}} = 0$$

$$H_a: \rho_{\text{MRI-NPtest}} \neq 0.$$

For this analysis, we will use Spearman correlations, Pearson correlations, and/or multiple regression.

The 3rd secondary hypothesis involves comparing the ability of regular MRI and VMRI to predict neurocognitive injury. The 3rd secondary hypothesis is:

Cortical gray matter and hippocampal volume will demonstrate a more significant correlation with executive and memory cognitive functions than the correlation of WML or lacunar infarcts with these same cognitive functions.

The statistical analysis will not involve a formal hypothesis test, but in statistical terms the hypothesis can be written as:

$$H_0: \rho_{\text{MRI-Nptest-Vol}} - \rho_{\text{MRI-Nptest-Reg}} = 0$$

$$H_a: \rho_{\text{MRI-Nptest-Vol}} - \rho_{\text{MRI-Nptest-Reg}} \neq 0.$$

For this analysis, we will descriptively compare Spearman or Pearson correlations.

The last secondary hypothesis involves randomizing 36 people who had a baseline WAIS-III PIQ score  $\leq 90$  to two treatment groups. We will treat one group with transfusion for 6 months and the other group with standard care for six months. After the six months of treatment we will perform a before and after comparison of the WAIS-III PIQ results, using within subject WAIS-III PIQ change scores as the outcome. We expect that on average patients who receive transfusion will show at least a five-point improvement when retested after six months of transfusion. Although this secondary hypothesis expresses the expected direction of effect independently of the observed affect in the control group, the statistical analysis will follow common practice and first use a 2-sided hypothesis test with an alpha of 0.05 to compare the mean within subject WAIS-III PIQ change score in the two groups. Second, we will calculate a 95% CI for the true effect of transfusion on WAIS-III PIQ within subject change scores for the group who received transfusion. We will use either a t-test, a Wilcoxon Two-Sample test, or a regression model to test the hypothesis. For statistical analysis we can express this secondary hypothesis as the mean within subject change score in WAIS III PIQ for the transfusion group will be different than the mean within subject change score in the control group:

$$H_0: \mu_{\text{diff, trt}} - \mu_{\text{diff, control}} = 0.$$

$$H_a: \mu_{\text{diff, trt}} - \mu_{\text{diff, control}} \neq 0.$$

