## 1 SYNOPSIS

Title: Neuropsychological Dysfunction and Neuroimaging Abnormalities in Neurologically Intact Adult Patients With Sickle Cell Disease (SCD)

CSCC Protocol Chair: [name].

Intervention: In Phase I, approximately 156 subjects will participate in a cross-sectional study consisting of screening questionnaires, a neuropsychological testing battery, and MRI testing. In Phase II, a subset of approximately 30 participants will be asked to participate in a transfusion intervention. Half will be randomized to undergo a chronic transfusion regimen for six months, and the other half will be treated with standard care alone, guided by their disease symptoms.

Objectives:
 
Primary objective(s): To determine the extent of neurocognitive dysfunction in neurologically asymptomatic adult patients with sickle cell disease.
 
Secondary objective(s): To determine the association between neurocognitive dysfunction and imaging abnormalities.

Hypotheses/Estimates:
 
Primary hypothesis: Neurocognitive testing in neurologically asymptomatic adult sickle cell patients will be abnormal compared to community controls.
 
Secondary hypotheses:
 
 
1. Neurologically intact adults with SCD will have significantly lower scores on other neuropsychological (NP) tests of executive function than adult controls.
 
2. A larger percentage of adult patients with abnormal MRIs will have abnormal NP testing than those with normal MRIs.
 
3. Volumetric MRI will detect brain dysfunction in patients with abnormal neurocognitive tests but normal qualitative MRI.
 
4. Correction of anemia with transfusion therapy will improve the cognitive function in SCD patients with abnormal neurocognitive testing more than standard care.
 
 
Hypothesis testing will apply to the primary hypothesis only; all secondary hypotheses will address issues of estimation.

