
Criteria for Evaluation:
 
In the cross-sectional study, the primary endpoint is completion of baseline Wechsler Adult Intelligence Scale-Third Edition (WAIS-III) PIQ studies in 120 subjects and 36 controls. The secondary endpoints include completion of the entire baseline NP battery and MRI studies in 120 subjects and 36 controls. In the pilot intervention trial, the primary efficacy endpoint is completion of the transfusion protocol and demonstration of 5-point improvement in WAIS-III PIQ from the standard core group in 30 patients.

Study Design: This study is a cross-sectional investigation designed to compare neuropsychological function of adult neurologically normal HbSS/SB subjects with matched-peer controls. Additionally, a pilot intervention trial will randomize a subset of patients from the primary study to undergo either a chronic transfusion regimen or receive standard care alone, for six months.

Study Population: Neurologically intact adult subjects ages 21-55 years, with Hb SS/SB will be enrolled in the cross-sectional study. A subset of these subjects with WAIS-III PIQ scores less than or equal to 90 will be eligible for randomization in the pilot transfusion trial.

Sample Size: 120 subjects and 36 controls are needed to assess the primary endpoint of completion of baseline WAIS III PIQ studies. The secondary endpoints would include completion of the entire baseline NP battery and MRI studies in 120 subjects and 36 controls. Assuming a 20% attrition rate, 150 subjects and 45 controls will be recruited. After consent and randomization, the final secondary endpoint is completion of the transfusion protocol with 30 patients and demonstration of 5-point improvement in WAIS-PIQ due to transfusion above any improvement observed in a standard care group. Again, assuming a 20% attrition rate, 36 patients will be recruited.

**Title:** Neuropsychological Dysfunction and Neuroimaging Abnormalities in Neurologically Intact Adult Patients With Sickle Cell Disease (SCD)

**Data Analyses:** To test the primary hypothesis, we will use a GLM to model the data. At each site we will match the patients using a ratio of 10 patients to 3 community controls and control for site, age, sex, and education.

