### 6.1 PRIMARY HYPOTHESIS

Given the evidence that NP testing is abnormal in pediatric patients with SCD and precipitating risk factors continue or may cumulatively increase with age, we propose that NP functioning in neurologically asymptomatic adults with SCD will also be abnormal. Specifically, we believe that the mean score of adult patients with SCD on the WAIS-III PIQ scale will be at least one standard deviation below the mean score of a group of community controls matched for age and educational level.

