## 13 STATISTICAL ANALYSIS

### 13.1 SAMPLE SIZE

The primary comparison is a difference in mean scores on the WAIS-III PIQ between adult SCD patients and community-based controls, after adjustment for age and years of education. Our preliminary data in children showed that even patients with normal MRI studies had a mean WAIS-III PIQ score of 87 (with a standard deviation of 20), close to one standard deviation below the normative mean of 100. The patients with silent infarctions on MRIs had a mean score of 75 (with a standard deviation of 11). We therefore would predict that our population of adults, some of whom will have abnormal MRI studies, will have a mean score of 85 or less and a standard deviation of 15. Although there are limited data, we would expect that the community control group of similar age and education level will have a mean of 100 with a standard deviation of 15. The discussion and tables below illustrate sample sizes (and associated power calculations) needed in order to detect varying magnitudes of differences in the mean score of our patients from the control group, with two different assumptions about the standard deviations. The calculations presented are based on the assumption that the ratio of patients to controls will be roughly 3:1.

For power calculations and statistical analysis, the primary hypothesis, adult SCD patients will have a mean WAIS III PIQ different from the mean of the community based control group adjusted for site, sex, age and years of education can be expressed:

$$H_0: \mu_{\text{control}} - \mu_{\text{SCD}} = 0$$

$$H_a: \mu_{\text{control}} - \mu_{\text{SCD}} \neq 0.$$

Although we will use a GLM to test the primary hypothesis, we used a 2-sample comparison t-test framework for power calculations. If the matching ensures homogeneity between the SCD patients and the control group except for SCD status, then for any choice of power the necessary sample size for the GLM will be smaller than what is predicted in this sample size analysis. To estimate the sample size needed per group to detect a 15 percentage point difference in two unequally sized groups using a 2-sided t-test (see Table 13.1), we used the following approximate sample size calculation algorithm:

$$1) \text{ Calculate } m: m = \frac{2(z_{1-\alpha/2} + z_{1-\beta})^2 \sigma^2}{|\mu_1 - \mu_2|^2}.$$

2) Let  $n_1$  = sample size for group 1, and  $n_2$  = sample size for group 2.

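### The primary model adjusts for site, age, sex and education in three places, but section 13.2 makes that adjustment conditional and leaves the final model to unspecified selection

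*Protocol*

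**What the plan says.** The Synopsis confines formal testing to one question: "Hypothesis testing will apply to the primary hypothesis only; all secondary hypotheses will address issues of estimation". Section 13.2 tests it two-sided at alpha 0.05.

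The model for that test is described in four places:

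- **Synopsis, Data Analyses.** At each site the plan is to "match the patients using a ratio of 10 patients to 3 community controls and control for site, age, sex, and education". No condition is attached.
- **Section 8.2.** After describing the matching grid, it says a GLM will in addition control for the same four factors, and refers to 13.2 for detail. Again there is no condition.
- **Section 13.1.** The hypothesis is that the SCD mean is "different from the mean of the community based control group adjusted for site, sex, age and years of education". The opening sentence of the same section, however, names only age and years of education.
- **Section 13.2.** Patients are matched 3:1, "but if necessary we will still statistically control for site, age, sex, and education". Then: "Model selection techniques will be used to determine the most parsimonious models". The null hypothesis is written in adjusted means taken from the final model.

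Section 13.2 also says that the first secondary hypothesis, on the other neuropsychological tests, is analysed in the same way.

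**The concern.** Sections 8.2 and 13.2 cannot both be followed as written. Under the Synopsis, 8.2 and the hypothesis in 13.1, the four factors are always in the model. Under 13.2 they enter if judged necessary and may leave if a more parsimonious model is found. Neither the criterion for necessity nor the selection rule is given, so two analysts who both follow the Protocol could report different primary results.

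This matters more here than in a randomised trial. Cases and community controls differ by more than disease status, and section 5.2.1 itself says that socio-economic factors may affect test performance and that controls are therefore matched on age and education. A covariate that misses a significance threshold with few controls has not been shown to be harmless. If it is dropped, any residual imbalance passes into the estimated SCD deficit, and the standard error from the chosen model ignores the choosing.

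This is not detail left for a later analysis plan. The Protocol states a selection procedure and ties the null hypothesis to its output. An analysis plan that fixed all four covariates would depart from 13.2; one that followed 13.2 would depart from the Synopsis and 8.2.

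**Working it through.** **1. The plan's own sample size.** Inputs from 13.1 and Table 13.1: difference 8, SD 15, two-sided alpha 0.05, power 0.80, k = 0.3.

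- m = 2(1.960 + 0.842)² × 15² / 8² = 55.19
- n1 = m(k + 1)/(2k) = 55.19 × 1.3/0.6 = 119.57, rounded up to 120
- n2 = 0.3 × 119.57 = 35.87, rounded up to 36
- Power at 120/36 = 0.801
- With 80% completion: 120/0.8 = 150 and 36/0.8 = 45

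The stated figures reproduce. They rest on an unadjusted t-test, so the choice of covariates does not alter them.

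**2. Type I error under each way of choosing the model.** Simulation with no true SCD effect: 120 cases, 36 controls, eight sites (section 8.1 says approximately eight), SD 15, and 4,000 runs per scenario (Monte Carlo SE about 0.35 percentage points). The covariate strengths (share of PIQ variance explained) and the education imbalance (cases lower than controls, in SD units) are assumptions; the Protocol gives neither. Backward elimination used p > 0.05. The last column takes the smallest SCD p-value over all 2⁴ = 16 covariate subsets.

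| Assumed variance explained by age, sex, education, site; education imbalance | All four fixed | Backward | BIC | None | Smallest p of 16 |
|---|---|---|---|---|---|
| 1, 1, 2, 2%; none | 4.7% | 5.0% | 4.8% | 4.8% | 7.6% |
| 2, 1, 10, 4%; none | 5.0% | 5.4% | 5.0% | 5.0% | 9.9% |
| 1, 1, 2, 2%; 0.2 SD | 5.0% | 5.1% | 5.2% | 5.1% | 9.0% |
| 1, 1, 2, 2%; 0.4 SD | 5.5% | 7.1% | 6.8% | 6.5% | 11.3% |
| 1, 1, 5, 2%; 0.3 SD | 4.8% | 5.6% | 5.6% | 6.3% | 10.5% |
| 2, 1, 10, 4%; 0.3 SD | 4.6% | 5.2% | 5.3% | 8.1% | 14.0% |

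**3. Hand check of one cell** (last row, no adjustment).

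- Bias = 15 × √0.10 × 0.3 = 1.42 points
- SE = 15 × √(1/120 + 1/36) = 2.85
- Bias/SE = 0.50
- Rejection rate = P(Z > 1.46) + P(Z < −2.46) = 0.072 + 0.007 = 7.9%, against 8.1% simulated

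**4. Reading the table.** The fixed model is nominal throughout. A mechanical rule does little harm when the groups are balanced. It does most harm when a covariate is weak enough to be dropped but imbalanced (fourth row). The last column is an upper bound on open choice, not a prediction of what the analysts would do.

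**5. Power of the fixed model.** With a true difference of 8, the second row's covariates and 2,000 runs, power was 85.7% with all four fixed and 81.1% with none.

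**The case against.** The strongest reply is that the matching already does most of the work. Section 8.2 matches within site, sex, age group and education level. It provides a control for non-empty cells that end with fewer than three cases, and it has a specific rule for the broad category above 12 years: the control should reflect the education of the three cases. A separate simulation that built this matching in (120/32, eight sites, 3,000 runs, up to one year of excess schooling for controls in the top category) gave 4.0-5.4% for the full model, 4.3-5.9% for backward selection and 4.3-5.1% with no adjustment. The worst unadjusted bias was about 0.6 points, which is small beside the 8 points the study is sized to detect. This stands as a limit on size. It does not remove the contradiction, because 8.2 plans adjustment in addition to matching.

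It can also be said that 13.2 never states outright that selection acts on these four covariates; it might concern interactions or functional form. That is possible. But they are the only covariates named, and the sentence follows directly on the conditional clause about them.

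Two stronger readings are not supported:

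- A reader might infer from the enrolment of 120 cases and 32 controls (3.75:1 rather than 3:1) that the groups are imbalanced. A ratio of group sizes says nothing by itself about covariate balance.
- A reader might infer that the test is wrong because section 6.1 expects that "the mean score of adult patients with SCD on the WAIS-III PIQ scale will be at least one standard deviation below the mean score" while the null is zero difference. Section 13.2 openly tests zero, two-sided, and nowhere says that rejection would establish a one-SD gap.

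**Conclusion.** The Protocol states its primary model inconsistently, and the version in 13.2 lets the data choose the model behind the only test the Synopsis treats as confirmatory. That holds on the text alone.

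The numerical consequence is modest and conditional. Type I error is about 5% if matching achieved good balance, about 5-7% for mechanical backward or BIC selection under an assumed residual education imbalance of 0.2-0.4 SD, and about 8-14% only if the covariate subset is chosen freely. The Protocol reports neither the achieved balance nor the covariate strengths, so these are ranges under assumptions, not estimates for this study.

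A reader might take the point to mean that the primary p-value is badly inflated, or that the comparison may be left wholly unadjusted. Neither follows. Mechanical selection stays close to nominal, and 13.2 writes its null in adjusted means, so complete omission of the covariates is the least natural reading. No sample-size figure is affected.

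**What to change.** - Prespecify one primary model: PIQ = SCD status + site + age + sex + years of education, with all terms retained whatever their p-values.
- In 13.2, delete the conditional clause and the model-selection sentence for the primary test and for the first secondary hypothesis, which uses the same analysis. Alternatively, confine reduced models to labelled sensitivity analyses.
- Make the opening sentence of 13.1 name the same four factors as the hypothesis below it.
- Report the adjusted difference with its 95% CI.

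Cost: wording, plus 7 + 1 + 1 + 1 = 10 degrees of freedom with eight sites. With 152 enrolled, 152 − 2 = 150 remain after intercept and SCD status, and 140 after the covariates. The sample size does not change. Section 10.7 places database finalisation and analysis after the last Phase II assessments, so under that timetable the model can still be fixed beforehand.
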